A Comparison of Horizontal and Vertical Bitewing Radiographs in Detecting Approximal Caries and Interdental Bone Loss in Posterior Teeth: A Diagnostic Accuracy Randomized Cross-Over Clinical Trial

NCT04341636

February 20, 2020

Principal Investigator:

[name]

Departments of Dental Public Health and Periodontology
King Abdulaziz University, Tufts University, Harvard University

Co-Investigators:

[name], [name]
Faculty of Dentistry, King Abdulaziz University

1. Background and Rationale

Bitewing radiographs are a standard diagnostic tool in dental practice, primarily used to detect approximal caries and evaluate interproximal alveolar bone levels. Traditionally, horizontal bitewings have been widely used for these purposes. However, they have limitations in visualizing vertical bone loss, furcation involvement, and root caries.

Vertical bitewing radiographs, by contrast, provide greater visibility of the apico-coronal dimension and root structures, making them potentially more effective for diagnosing periodontal conditions and deeper carious lesions. This study aims to compare the diagnostic accuracy of vertical versus horizontal bitewing images in detecting caries and bone loss in posterior teeth.

2. Objectives

Primary Objective

- To compare the accuracy of vertical versus horizontal bitewing radiographs in detecting approximal caries and alveolar bone loss.

Secondary Objective

- To evaluate the effectiveness of both imaging modalities in identifying furcation involvement.
- To assess the diagnostic clarity and patient suitability for each radiographic approach.

Material and methods:

3. Study Design

This is a two-arm, randomized crossover clinical trial comparing vertical and horizontal bitewing radiographs. The study was conducted at the Faculty of Dentistry, King Abdulaziz University.

Type of Study: Open-label, randomized crossover clinical trial

Study Setting: Faculty of Dentistry, King Abdulaziz University

Registration: ClinicalTrials.gov (NCT04341636)

Ethical Approval: KAU Ethics Committee (#053-06-17)

4. Participants

Inclusion Criteria:

- Age ≥ 18 years
- Presenting for treatment at KAU dental clinics
- Presence of posterior teeth and canines in each quadrant
- No acute periodontal infection
- Non-smokers
- Full ability to open mouth and tolerate X-ray procedures

Exclusion Criteria:

- Systemic conditions complicating treatment
- Pregnancy or lactation
- Prosthesis obscuring CEJ or caries borders
- Gag reflex or any contraindication to X-ray
- Refusal to participate

5. Interventions

Each participant received:

- Four horizontal bitewing radiographs (control)
- Four vertical bitewing radiographs (experimental)
- Radiographs were taken using a standardized film holder and a 3-mm orthodontic wire attached to the sensor for magnification calibration.

Observers included two restorative specialists (for caries) and two periodontists (for bone loss), all blinded to group assignments.

6. Measurements

- Caries Assessment:

Evaluated using a 5-point diagnostic confidence scale and a secondary clarity scale.

- Bone Loss & Furcation:

Measured from the CEJ to the alveolar crest using calibrated software. Furcation involvement was assessed using a 5-point scale.

- Intra- and Inter-Observer Agreement:

Evaluated with Kappa statistics and intra-class correlation coefficients.

7. Sample Size Calculation

- **Software:** G*Power 3.1.9

- Effect size: 2.1 mean difference

- SD: 5.2

- Power: 80%

- Alpha: 0.05

- Required Sample: 20 patients

8. Statistical Analysis

Statistical Analysis

Software:

Data will be analyzed using IBM SPSS Statistics version 23.0 (IBM Corp., Armonk, NY, USA) and ROC analysis will be performed using MedCalc or equivalent software for diagnostic

accuracy assessment.

8.1 Analysis Population:

All radiographs captured for the 20 enrolled participants (160 total bitewing images: 80 vertical, 80 horizontal) will be included. Both intention-to-treat and per-protocol analyses will be conducted. All images were anonymized, and evaluators were blinded to image type and patient identity.

8.2 Primary Analysis:

Primary Endpoints:

- Detection of approximal caries (presence and clarity)
- Alveolar bone level measurements (in mm)
- Presence and clarity of furcation involvement

Tests for Diagnostic Accuracy:

- **Receiver Operating Characteristic (ROC) Analysis:**

ROC curves were plotted for each evaluator for both vertical and horizontal bitewings.

The Area Under the Curve (AUC) was computed to assess diagnostic accuracy compared to the “gold standard” (combined clinical and radiographic diagnosis).

- AUC values close to 1.0 indicate higher accuracy.
- Comparisons of AUCs between vertical and horizontal bitewings were conducted using DeLong’s test.
- **Sensitivity and Specificity:** These were calculated for each radiographic method in detecting caries and furcation involvement. 95% confidence intervals were provided.

8.3 Observer Reliability:

- **Intra-Observer Agreement:** Measured using **Weighted Kappa coefficients** for repeated readings of the same radiographs by the same observer at two time points.

- **Inter-Observer Agreement:** Measured using **Intraclass Correlation Coefficient (ICC)** for bone level measurements and **Weighted Kappa** for caries and furcation rating scores between observers.

Interpretation of Kappa values:

- < 0.20: Poor
- 0.21–0.40: Fair
- 0.41–0.60: Moderate
- 0.61–0.80: Substantial
- 0.81–1.00: Almost perfect

8.4 Comparative Tests Between Vertical and Horizontal Bitewings:

- **Wilcoxon Signed-Rank Test:** Used to compare the mean alveolar bone loss measurements (mesial, distal, and total) between vertical and horizontal bitewings (non-parametric paired comparison).
- **McNemar Test:** Applied to assess paired binary outcomes (e.g., presence vs. absence of caries or furcation involvement) between imaging modalities.
- **Chi-Square Test:** Used to compare proportions of overlapping contacts and furcation detection in both modalities.
- **Descriptive Statistics:**
 - Mean \pm standard deviation (SD) for continuous variables (e.g., bone level)
 - Frequencies and percentages for categorical variables (e.g., tooth type, gender distribution)

8.5 Handling of Missing Data:

- Missing image evaluations (if any) were addressed via sensitivity analysis using pairwise deletion, given the minimal expected rate due to controlled data acquisition and blinded

scoring.

8.6 Effect Size Reporting:

- For Wilcoxon and McNemar tests, effect sizes (r) were reported.
- For ROC analysis, 95% CI of AUCs and comparison P-values were provided.

9. Expected Outcomes

- Vertical bitewings will show higher sensitivity in detecting furcation involvement.
- Vertical bitewings will provide better diagnostic accuracy for approximal caries and alveolar bone loss.
- Vertical bitewings will have superior intra- and inter-observer reliability in detecting pathology.

10. Ethical Considerations

- All participants provided informed written consent.
- Ethical approval was secured from local ethics board.
- All data were anonymized and securely stored.
- Participants had the right to withdraw at any time without consequences.

11. Timeline

Phase	Duration
Ethical Approval	Completed
Participant Recruitment	2 months
Radiograph Collection	2 months
Data Analysis	1 month

Phase	Duration
Manuscript	1 month

12. Dissemination Plan

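### Imaging order is the only factor this crossover can randomise, yet no comparison uses it; the pooled tests stay valid on average but lose precision to any order effect and have no protection against a chance-uneven split

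*Combined protocol and SAP*

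**What the plan says.** Section 3 describes the design: "This is a two-arm, randomized crossover clinical trial comparing vertical and horizontal bitewing radiographs". It also gives the masking: "Type of Study: Open-label, randomized crossover clinical trial". Section 5 lists what each participant receives: "Four horizontal bitewing radiographs (control") and "Four vertical bitewing radiographs (experimental"). Section 8.1 confirms that all 20 participants contribute to both views: "160 total bitewing images: 80 vertical, 80 horizontal".

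Section 8.4 compares the views with two paired tests. The Wilcoxon signed-rank test is "Used to compare the mean alveolar bone loss measurements (mesial, distal, and total) between vertical and horizontal bitewings (non-parametric paired comparison"). The McNemar test is "Applied to assess paired binary outcomes (e.g., presence vs. absence of caries or furcation involvement) between imaging modalities". A chi-square test covers overlapping contacts and furcation detection. Section 8.2 compares AUCs by DeLong's test and reports sensitivity and specificity for each view.

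The documents do not say what was randomised, how the sequence was generated, how many participants had each order, how long separated the two sets, or whether the order was recorded. Sections 8.1 to 8.6 contain no sequence term, no period term and no order-based sensitivity analysis.

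**The concern.** In a two-period crossover, each vertical-minus-horizontal difference holds the effect of view plus or minus the effect of being imaged second. Pooling the two orders treats first and second sets as exchangeable.

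The anatomy should not change between sets, but image quality can. By the second set the operator has already positioned the sensor in that mouth and may correct angulation or contact overlap. The participant has already had four exposures and may tolerate placement less well. Quality bears directly on the endpoints: 8.2 makes clarity of caries and furcation part of the primary endpoints, and 8.4 compares contact overlap. Blinded reading does not remove such an effect, because it is already in the image.

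At stake is precision in a trial of 20. If the two orders are unequal in number, part of an order effect would also be read as a difference between views. The plan as written could neither detect nor remove it.

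**Working it through.** **Inputs.** n = 20, mean difference 2.1 and SD 5.2 come from Section 7. The analysis is taken at patient level. The period shift and the use of simple randomisation are assumptions, since the documents give neither.

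**The plan's own figure.** Section 7 gives 20 patients for "Effect size: 2.1 mean difference". Taking 5.2 as the SD of paired differences, the standardised difference is 2.1/5.2 = 0.40. A two-sided paired t-test then needs 51 patients and has power 0.40 with 20 (signed-rank about 0.39). The figure of 20 is recovered if 5.2 is the SD within each view and the two views correlate at about 0.81, which the plan does not state. That is a separate matter. It matters here only because it explains the low baseline power below.

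**Model.** Let p be the period shift in SDs of the paired difference. The expected difference is (view effect + p) in one order and (view effect − p) in the other. With n1 and n2 patients in the two orders and f = n1/20:

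- shift in the pooled estimate = p × (n1 − n2)/20;
- variance seen by the pooled test = SD² × [1 + 4f(1 − f)p²].

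**10:10 split.** The shift is zero and the SE is multiplied by √(1 + p²). Power and error rates in the tables are from simulation of the signed-rank test.

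| p | SE multiplier | Type I error | Power at 2.1/5.2 |
|---|---|---|---|
| 0 | 1.00 | about 0.05 | about 0.39 |
| 0.25 | √1.0625 = 1.03 | about 0.045 | about 0.37 |
| 0.5 | √1.25 = 1.12 | about 0.025 | about 0.30 |
| 1 | √2 = 1.41 | about 0.005 | about 0.12 |

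A linear analysis with a sequence term keeps power at about 0.40 throughout.

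**Chance of an uneven split.** From Binomial(20, 0.5): exactly 10:10 has probability 0.176, 7:13 or worse 0.263, and 6:14 or worse 0.115.

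**6:14 split.** The shift is p × 8/20 = 0.4p.

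| p | Shift if SD = 5.2 | Share of 2.1 | Type I error |
|---|---|---|---|
| 0.25 | 0.4 × 1.3 = 0.52 | 25% | about 0.07 |
| 0.5 | 0.4 × 2.6 = 1.04 | 50% | about 0.09 |
| 1 | 0.4 × 5.2 = 2.08 | 99% | about 0.16 |

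The sequence-adjusted analysis keeps type I error at about 0.05.

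**Averaged over all splits.** With order assigned by coin flip, each patient's null difference is symmetric about zero. Simulated type I error of the pooled signed-rank test was 0.047 to 0.049 for p from 0 to 1, with mean bias near zero.

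**Price of adjusting.** At 6:14 the adjusted SE is 5.2 × √(1/56 + 1/24) = 1.27, against 5.2/√20 = 1.16 unadjusted. If there is no period effect, power is about 0.35 against 0.39.

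**The case against.** The strongest reply is that randomising order already does its work by design. Under simple randomisation the signed-rank test holds its 5% level and the estimate is unbiased on average. This stands. A reader might infer from the missing order term that the pooled tests are invalid or the results systematically biased. The documents do not support that: the shift and the raised error rates apply only given an uneven split, and no split is reported.

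Second, the period effect may be small. CEJ-to-crest distance is anatomical, and Section 5 specifies a standardised holder and a 3-mm calibration wire. Shifts of 0.5 and 1 SD would be 2.6 and 5.2 on the Section 7 scale, both larger than the 2.1 the trial was planned to detect. This also stands as a limit on size: at 0.25 SD and an even split the SE rises by only 3%, and at 0.1 SD by 0.5%. The holder and wire address placement and magnification, though. They do not guarantee equal angulation, overlap or tolerance in first and second sets.

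Third, because participants attend for dental treatment, a reader might infer that treatment fell between the two sets. The documents are silent on the interval, so that is not established. What can be said is that the interval is not stated.

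**Conclusion.** The point holds as one of efficiency and of protection against chance imbalance. The trial randomises, by inference, the order of imaging, and no listed comparison uses that order. The cost is negligible if the period effect is below about 0.25 SD and the split near even. It is material if the effect reaches 0.5 SD (SE up 12%, power about 0.39 to 0.30) or if the split is as uneven as 6:14, which has a probability of about 12% under simple randomisation.

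These sizes rest on an additive period effect, an assumed range for it, and 5.2 read as the SD of paired differences. They were worked out only for the bone-level comparison. The same mechanism applies to McNemar, chi-square and DeLong, but sizing it would need rates that the documents do not give. Nothing in the documents shows that a period effect or an uneven split occurred, or that order went unrecorded.

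**What to change.** **Section 3.** State that order is the randomised factor and how the sequence is generated. Allocate the two orders 10:10 in blocks and record the order for each participant. Parts of the document are in the past tense. If the images are already taken, report the split obtained; if order was not recorded, report that as a limitation. State the interval between the two sets and whether treatment could fall between them.

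**Section 8.4.** For bone level, form one vertical-minus-horizontal difference per patient and allow for sequence. One way is a linear model with a sequence term coded +1/−1, so that the intercept averages the two orders equally. The other is the matching rank test, a rank-sum comparison of first-minus-second differences between the two orders. For binary outcomes, use the Mainland-Gart/Prescott form in place of McNemar. Report the estimated period effect with its interval.

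**Section 8.2.** Add an AUC comparison stratified by order as a sensitivity analysis to DeLong's test.

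**Cost.** An allocation list, one recorded variable and a few lines of text, with no extra patients or exposures. The analysis spends one degree of freedom and loses a little power if the split is uneven and there is no period effect (about 0.35 against 0.39 at 6:14). A balanced allocation largely avoids that loss.

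### The single power statement in Section 7 does not cover the AUC, sensitivity/specificity and McNemar comparisons that serve the primary objective, and the outcome it does refer to is not named

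*Combined protocol and SAP*

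**What the plan says.** Section 7 (Sample Size Calculation) names G*Power and gives "Effect size: 2.1 mean difference", an SD of 5.2, 80% power, alpha 0.05 and "Required Sample: 20 patients". It does not state the endpoint, the unit, the test, the sidedness, whether 5.2 is the SD of one method or of the paired difference, or any correlation between methods.

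The primary objective in Section 2 is "To compare the accuracy of vertical versus horizontal bitewing radiographs in detecting approximal caries and alveolar bone loss". Section 3 describes a "two-arm, randomized crossover clinical trial comparing vertical and horizontal bitewing radiographs", so the comparison is paired.

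Section 8.2 lists three primary endpoints: caries detection (presence and clarity), bone level in mm, and furcation (presence and clarity). Accuracy is to be assessed by ROC analysis against a reference diagnosis ("Comparisons of AUCs between vertical and horizontal bitewings were conducted using" DeLong's test), together with sensitivity and specificity. Section 8.4 adds McNemar's test for paired binary outcomes and a Wilcoxon signed-rank test for bone level.

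On measurement scales, Section 6 says of caries: "Evaluated using a 5-point diagnostic confidence scale and a secondary clarity scale". Of furcation it says: "Furcation involvement was assessed using a 5-point scale". Section 8.2 puts the AUC on a scale that ends at one: "AUC values close to 1.0 indicate higher accuracy".

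**The concern.** This is a diagnostic accuracy trial, and its accuracy question is answered by AUCs, sensitivity, specificity and paired detection rates. The plan gives no AUC, prevalence, sensitivity or discordance assumption anywhere, so none of these comparisons has a power justification. The one power figure concerns a difference in means with an SD too large for the ratings and accuracy measures as the document describes them.

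The stake is interpretation. If a DeLong or McNemar test is not significant, a reader who sees 80% power and a required size of 20 may conclude that the two views were shown to be equally accurate. Nothing in the calculation supports that conclusion.

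This is separate from whether 20 follows from the stated inputs. Repairing that arithmetic would still leave the accuracy comparisons without a power statement.

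**Working it through.** **1. The plan's own figure.** Inputs from Section 7: difference 2.1, SD 5.2, alpha 0.05, power 80%, N = 20. Sidedness is not given, so both were tried, using a paired t-test with the noncentral t distribution.

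- If 5.2 is the SD of the paired difference, the standardised effect is 2.1/5.2 = 0.404. Two-sided, 80% power needs 51 patients, and 20 patients give 40%. One-sided, it needs 40 patients, and 20 give 54%.
- If 5.2 is the SD of one method, the SD of the difference is 5.2 × √(2(1 − ρ)). For 80% power at N = 20 two-sided, the standardised effect must be 0.660, so the SD of the difference must be 2.1/0.660 = 3.18 and ρ = 1 − 3.18²/(2 × 5.2²) = 0.81. One-sided, the corresponding values are 0.577, 3.64 and ρ = 0.755, or about 0.76.

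So N = 20 is reproduced only with a correlation that the document does not state.

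**2. Can SD 5.2 belong to a rating or an accuracy measure?** A bounded variable has an SD of at most half its range. For a sample SD with n = 20, multiply by √(20/19) = 1.026.

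| Quantity | Range | Largest sample SD |
|---|---|---|
| Single 5-point rating (coded 1 to 5, assumed) | 4 | 2 × 1.026 = 2.05 |
| Paired difference of two such ratings | 8 | 4 × 1.026 = 4.10 |
| AUC, sensitivity, specificity on 0 to 1 | 1 | 0.5 × 1.026 = 0.51 |
| Paired difference of these | 2 | 1 × 1.026 = 1.03 |

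All four are below 5.2. A mean difference of 2.1 is also impossible for an AUC or a proportion on the 0 to 1 scale. Bone level in mm is the only endpoint in 8.2 stated as a continuous measurement. A difference in mean mm between views shows that they read differently, not which is closer to the reference diagnosis.

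**3. What 20 patients might detect in AUC (illustration).** The document gives none of the following, so all are assumed: 24 surfaces per patient (20 × 24 = 480); baseline caries AUC 0.75 to 0.80; 160 molars for furcation with baseline AUC 0.65 to 0.75; correlation r between views 0.4 to 0.6; design effect (DE) for clustering 1.5 to 2; two-sided 5%; 80% power.

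The Hanley-McNeil variance is s² = [A(1 − A) + (n₁ − 1)(Q₁ − A²) + (n₀ − 1)(Q₂ − A²)]/(n₁n₀), where n₁ and n₀ count positive and negative sites, Q₁ = A/(2 − A) and Q₂ = 2A²/(1 + A). The standard error of the difference satisfies SE² = DE × (s₁² + s₂² − 2r s₁s₂). The smallest detectable gain d solves d = (1.96 + 0.84) × SE.

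Example: 20% prevalence gives n₁ = 96 and n₀ = 384. With A = 0.75, r = 0.4 and DE = 2, s₁ = 0.0306 and, at AUC 0.871, s₂ = 0.0241. Then SE = √(2 × (0.0306² + 0.0241² − 0.8 × 0.0306 × 0.0241)) = 0.0431, and 2.80 × 0.0431 = 0.121, which matches the gain of 0.121.

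| Setting | Smallest detectable AUC gain |
|---|---|
| Caries, 30–40% prevalence | about 0.06–0.10 |
| Caries, 20% | about 0.08–0.12 |
| Caries, 10% | about 0.11–0.16 |
| Caries, 5% | about 0.15–0.21, or unattainable |
| Furcation, 16 positive molars of 160 | about 0.20–0.29, or unattainable (baseline 0.75, DE 2) |

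**4. McNemar (illustration).** With discordant proportions p₁₀ and p₀₁ among diseased sites, sum p and difference δ, n = (1.96√p + 0.84√(p − δ²))²/δ². For 15% against 5%, (0.877 + 0.367)²/0.01 gives 155 diseased sites, treated as independent. For 20% against 5% it is 85. At 20% prevalence, 480 surfaces would contain 96. Adequacy therefore depends on assumptions the plan does not make.

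**The case against.** Several stronger readings are tempting, and the objections to them stand.

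- **That the outcome must be bone level.** This is inference by elimination, and the elimination is incomplete. Ratings summed over a patient's surfaces, or sensitivity in percentage points, could have an SD of 5.2, and the range of the clarity scale is not given. The document mentions no summed or percentage score, but it does not exclude one. None of these would turn a paired-means calculation into a power calculation for DeLong or McNemar.
- **That the plan claims 80% power for every primary endpoint.** No sentence says so. Section 7 is silent on scope, and a reader might infer wider coverage only because no other power figure appears.
- **That the plan intends to claim equal accuracy from a null result.** It does not. Section 9 states only expectations that vertical views will do better. Sections 8.2 and 8.6 already provide 95% confidence intervals for sensitivity, specificity and AUC, which partly guard against that misreading.
- **That only large AUC differences can be detected.** This depends on prevalence and clustering. Participants present for treatment, so caries prevalence may be high, and at 30–40% the detectable gain falls to about 0.06–0.10.
- **That the furcation gap is a failure on a primary aim.** Furcation is a secondary objective in Section 2 but a primary endpoint in 8.2. If it is secondary, missing power matters much less.

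**Conclusion.** The concern holds in a limited form. The stated 80% power does not cover the accuracy comparisons in 8.2 and 8.4. Two grounds establish this: the SD ceilings, for single ratings and for accuracy measures on the 0 to 1 scale; and, on any scale, the fact that a paired-means calculation is not a power calculation for DeLong or McNemar. Neither ground needs the assumed prevalence, surface count or clustering.

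Which outcome Section 7 used is not established. Even for that outcome the 80% is not safe as it stands: the power is about 40% two-sided or 54% one-sided if 5.2 is the SD of the paired difference, and 80% only with an unstated correlation of about 0.81 (two-sided) or 0.76 (one-sided) if 5.2 is the SD of one method.

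The detectable AUC gains are illustrations resting wholly on assumed inputs. They show how widely the answer varies, and they do not establish that the trial is too small.

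**What to change.** Keep N at 20 and change the wording as follows.

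1. In Section 7, state the outcome, unit, test, sidedness and type of SD (one method or paired difference) that were used, and restate the power for that outcome. Simply attaching the existing 80% to bone level would make an ambiguous figure definite and possibly wrong.
2. State that this figure does not apply to the AUC, sensitivity/specificity or McNemar comparisons. Give the smallest AUC difference detectable with 80% power at 20 patients, for caries and for furcation, with the assumed number of sites, prevalence, baseline AUC, correlation and design effect listed.
3. In 8.2, add a confidence interval for the paired difference between views to the 95% intervals already planned. State that a non-significant DeLong or McNemar result will be interpreted through these intervals and reported as inconclusive, not as equal accuracy.
4. Reconcile the status of furcation between Section 2 and 8.2.

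The cost is wording and a short calculation, with no extra patients or images. The downside is a less favourable stated power.

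### Section 7's 20 patients at 80% power cannot be reproduced from its listed inputs for the paired crossover design without an assumption that it does not state

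*Combined protocol and SAP*

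**What the plan says.** Section 7 is the documents' only justification for the size of the trial. It names G*Power 3.1.9 and lists "Effect size: 2.1 mean difference", an SD of 5.2, power of 80% and alpha of 0.05. It ends with "Required Sample: 20 patients".

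The design is set out elsewhere in the same document:

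- Section 3: "This is a two-arm, randomized crossover clinical trial comparing vertical and horizontal bitewing radiographs".
- Section 5: every participant has both image types, "Four horizontal bitewing radiographs (control)" and "Four vertical bitewing radiographs (experimental)".
- Section 8.1: the analysis covers "160 total bitewing images: 80 vertical, 80 horizontal" from the 20 participants.
- Section 8.4: bone loss is compared by the Wilcoxon signed-rank test "between vertical and horizontal bitewings (non-parametric paired comparison)", and binary outcomes by the McNemar test.

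Section 7 does not give the test, whether alpha is one- or two-sided, the endpoint and its unit, or the unit of analysis. It also does not say what 5.2 describes, or whether any correlation or intraclass correlation (ICC) was assumed. Section 8.2 names three primary endpoints. Only bone level is given in mm, but Section 7 does not tie the 2.1 to it.

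**The concern.** A difference of 2.1 against an SD of 5.2 is a standardised effect of about 0.40. In a paired comparison of one value per patient, 20 is too few for 80% power at that effect. Either the calculation used an input that is not written down, or the number does not belong to this design.

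The readings have very different consequences. If 5.2 is the SD of within-patient differences, the chance of missing a true difference of 2.1 is about 60% two-sided (46% one-sided), against the 20% that the plan implies. A null result could then be mistaken for evidence that the two image types perform alike. If 5.2 is really a variance, 20 patients are adequate or nearly so and only the label is wrong. A reader cannot tell which applies.

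**Working it through.** **Inputs.** From Section 7: difference 2.1, SD 5.2, alpha 0.05, target power 0.80, n = 20. From Section 5: four images of each type per patient. Sidedness is not given, so both are shown. Correlation (rho) and ICC values are assumptions, because the documents give none. Power is from the noncentral t distribution.

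**Step 1. Listed inputs only, paired.** Take 5.2 as the SD of within-patient differences: dz = 2.1/5.2 = 0.404, with noncentrality dz × √n on n − 1 df.

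| | Two-sided | One-sided |
|---|---|---|
| Patients needed | 51 (0.807; 0.799 at 50) | 40 (0.806; 0.797 at 39) |
| Power at 20 | 0.403 | 0.538 |
| dz needed for 80% at 20 | 0.660 | 0.577 |
| Difference detectable (dz × 5.2) | 3.43 | 3.00 |

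The stated 20 is not reproduced. The planned Wilcoxon signed-rank test has slightly less power under normality, about 38% to 39% two-sided at 20 patients by simulation.

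**Step 2. 5.2 as a per-modality SD, one value per patient.** SD of differences = 5.2 × √(2(1 − rho)). For 80% at 20 patients it must be 2.1/0.660 = 3.18, so rho = 1 − (3.18/5.2)²/2 = 0.813 two-sided. One-sided it must be 2.1/0.577 = 3.64, so rho = 0.755. Power at 20 (two-sided / one-sided) is 40% / 54% at rho 0.5, 60% / 73% at 0.7 and 77% / 87% at 0.8.

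**Step 3. Image pairs as the unit, four per patient.** SD of a patient's mean difference = s × √((1 + 3 × ICC)/4), where ICC is that of the pair differences and inference is on 20 patient means.

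- If s = 5.2 (SD of pair differences), 80% needs ICC ≤ (4 × (3.18/5.2)² − 1)/3 = 0.165 two-sided, or 0.32 one-sided.
- If 5.2 is a per-image SD, s = 5.2 × √(2(1 − rho)). The two-sided ICC limit is then 0.165 at rho 0.5, 0.29 at 0.6, 0.50 at 0.7 and 0.66 at 0.75. Below rho of about 0.25, no ICC of zero or more reaches 80%.

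**Step 4. Unpaired tests with SD 5.2.** These need 98 per group two-sided and 77 one-sided. If 77 is a count of images per modality, 77/4 = 19.25, which rounds up to 20 patients. This route ignores both the pairing and the clustering of images within patients.

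**Step 5. 5.2 as a variance.** SD = √5.2 = 2.28 and d = 2.1/2.28 = 0.921.

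- Unpaired, two-sided: 20 per group (0.810; 0.789 at 19).
- Paired, variance of the differences, two-sided: 12 patients suffice, and 20 give about 97%.
- Paired, per-modality variance, 20 patients, two-sided: 79% at rho 0 and 91% at rho 0.3.

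**The case against.** The strongest reply is that this is an omission in reporting, not a wrong number. Two images of the same sites in the same mouth may well be highly correlated, so rho near 0.8 cannot be ruled out. Section 8.1 counts images, so an image-level calculation is plausible, and one such route lands exactly on 20. Section 9 states a directional expectation, "Vertical bitewings will provide better diagnostic accuracy for approximal caries and alveolar bone loss", which would suit a one-sided test. A variance entered under an SD label would also explain the figure. One line from the G*Power record might close the matter.

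Much of this stands. A reader might infer from 51 patients and 40% power that the trial is underpowered or must recruit more. The documents do not support that, because they do not establish that 5.2 is the SD of within-patient differences.

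What does not stand is that the 80% is therefore justified. Section 7 gives its requirement in patients, labels 5.2 an SD, and states no correlation or ICC. An expectation of direction does not set a one-sided alpha. The unpaired routes to 20 do not match Sections 3 and 8.4.

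It is also fair to object that the planned bone-loss test is not a t-test. The t-test figures are therefore an approximation and should be labelled as one. The readings above are not exhaustive either: units based on sites, or averages over the two periodontists, are not worked through.

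**Conclusion.** The concern holds as one of reproducibility. For the paired crossover, 20 patients at 80% power do not follow from a difference of 2.1, an SD of 5.2 and alpha 0.05. The literal paired reading gives 51 patients two-sided or 40 one-sided, and about 40% or 54% power at 20. Every route to 20 that was examined needs an unstated correlation or ICC, a mislabelled SD, or a test that does not match the design.

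A power shortfall is not proven. Depending on what 5.2 is, two-sided power at 20 patients runs from well under 50% to about 97%. Confidence is high that the 80% is unsupported as written. No particular shortfall can be asserted without the G*Power record. The point must still be fixed, because nothing else in the documents supports the sample size.

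**What to change.** Keep the 20 patients. Check the G*Power record, including whether 5.2 was entered as an SD or a variance. In Section 7, state the endpoint and its unit, the test, sidedness, unit of analysis, what 5.2 is, and any correlation or ICC assumed. Then replace the 80% with the power that 20 patients give for the paired patient-level comparison:

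- **SD of within-patient differences.** Write: 'With 20 patients, power for a difference of 2.1 is about 40% (two-sided 5%, paired t-test used as an approximation to the planned Wilcoxon signed-rank test); 80% power is reached for a difference of about 3.4.'
- **Per-modality SD, per-image SD or SD of image-pair differences.** Give power over a stated range of correlation and ICC, as applicable. Where images are averaged, say that the figure assumes analysis of patient means, because Section 8.4 does not say how the four images per patient are combined.
- **Variance.** Correct the label (SD about 2.28) and restate the power for the paired design.

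If the record documents an assumption that gives 80% for the paired design, stating it closes the point.

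The cost is the wording of Section 7 only, with no extra patients. The stated power may become less favourable.
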